Also of concern with the use of chronic immunosuppression therapy in the ambulatory care setting are drug interactions. The calcineurin inhibitors and mTOR inhibitors, which are widely utilized immunosuppressants, are metabolized through the cytochrome P450 3A4/5 enzyme system, making them prone to interactions. Due to their effects on the renal and nervous system, these drugs are also frequently associated with pharmacodynamic drug interactions and drug-disease interactions. This includes interactions with classes of medications that are the most frequently prescribed in the outpatient setting, such as NSAIDs and ACE inhibitors. These interactions can result in an acute and dramatic reduction in renal function and electrolyte disturbances, particularly hyperkalemia.^{32,33} The impact of drug-related problems leading to graft loss on clinical and economic outcomes cannot be overstated. Annual death rates are more than three times higher in those with kidney allograft failure (9.4%), as compared to those with a functioning transplant (2.8%).³⁴ A well-functioning kidney transplant has also been shown to dramatically reduce the progression of cardiovascular disease and associated events.³⁵⁻³⁷ In other organ types, graft loss universally leads to either retransplant or death. In terms of cost, transplantation is highly cost-effective. However, due to high and varied peri-operative costs associated with this surgery, the break-even point can range from two to 11 years after transplant.^{38,39} Once a kidney transplant fails, patients return to dialysis and costs to provide care accrue at a significantly higher rate.^{40,41} Our research indicates that kidney transplant recipients that experience clinically significant medication errors spend five more days in the hospital for readmissions, costing more than \$18,000 per case.¹⁴ These data, taken in its entirety, establishes the need for innovative interventions designed to improve medication safety and reduce drug-related problems in transplant recipients, by decreasing medication errors, non-adherence and adverse drug events;¹⁰ Such medication safety improvements are needed to demonstrate significant progression in

the optimization of long-term graft outcomes and patient survival.

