4.2 Exclusion Criteria

- There are no exclusion criteria for patients in this study as recruitment is at the level of the VA site.
- All veterans meeting inclusion criteria will be monitored by the dashboard system and will be included in the outcomes assessment. Patients may enter or exit the study in a rolling manner, which will be accounted for during analyses.

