9.3.1 Primary outcome

The primary outcome for this study will include the overall rate of ER visits and hospitalizations, compared between the intervention and control groups. These encounters will be captured electronically throughout the 24-month study through the use of the CDW, stored in the VINCI environment. In addition, to ensure encounters are captured in a comprehensive manner, we will also link the VA CDW data to CMS (Medicare) claims data and capture non-VA ER and hospitalization encounters (after study completion). As most transplant patients are dual users and have Medicare

insurance benefits, this linkage will provide a more accurate assessment of these health care utilization.³ We expect ER visits and hospitalizations to significantly decrease within the intervention arm, towards the latter half (second 12-months) of the study due to a lag effect of the intervention on this outcome. This expectation is based on our previous research in this field and assessment of pharmacist interventions on medication safety and reduced adverse drug events requiring hospitalization. ER visits and hospitalizations will be assessed and compared as described in the statistical analysis plan. These will be defined based on encounter criteria within the CDW and CMS data: all-cause ER visits and all-cause hospitalizations leading to at least one overnight stay will be included as events.

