9.3.2 Secondary outcomes

Secondary assessment will include a cost benefit analysis. Overall health care costs accrued during the 24-month study, as well as those accrued in the 24-months prior to study initiation will be analyzed and compared between the control and intervention groups. Cost data will be standardized using the VA Health Economics Resource Center (HERC) definitions, which normalizes regional differences in costs due to variation in cost of living indices. As with the primary outcome, we will also acquire and link CMS claims data to gain a comprehensive assessment of costs, including those that accrue from non-VA care (after study completion). Costs will also be sub-analyzed into three predominant categories: inpatient costs, outpatient costs and pharmacy costs, as described in the statistical analysis plan. To fully assess if the intervention is has a direct monetary benefit, we will measure costs of the intervention will include estimates of time and resources to implement the dashboard and train and support the intervention site pharmacists. Similar to primary outcome, we expect that as ER visits and hospitalizations decrease within the intervention arm, there will be a corresponding decrease in overall costs as well, predominantly driven by inpatient costs. We expect this decrease to occur during the second 12 months of the study period, as the intervention is likely to have a lag effect on this outcome as well.

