9.4 Data Analyses

The data analysis will incorporate the intent-to-treat principle; namely, all participants enrolled in the intervention group will be included in the analysis and compared to all of the patients captured within the control group. If a patient dies, has graft loss or moves out of their study site, their data will be censored at that time point. For comparative statistical assessments within the utilization outcomes, the two groups will be compared using a generalized linear mixed models (GLMM) approach.⁵⁴ This approach allows for measurement of participants at different time points, clustering by study site, missing data under the assumption of missing at random (MAR), time varying or invariant covariates, and can also account for the effect of correlated longitudinal measurements within participants. In addition, GLMM accommodates a wide range of distributional assumptions such as dichotomous (e.g. binomial), count (e.g. Poisson), continuous

(e.g. Gaussian), and categorical or ordinal outcomes. For comparing the primary outcome (ED visit and hospitalization rates), we will use GLMM (with appropriate link function) with counts of these events as the outcome variable and intervention group (yes/no) as the primary independent variable. This analysis is equivalent to Poisson regression or negative binomial regression (in the case of over-dispersion), both special cases of GLMM. Additional adjustment covariables will be added to the model in a second set of analyses. Covariates will include patient sociodemographics: age, sex, race, comorbidities (using modified Elixhauser definitions), marital status and education. In these models, donor information (age, sex, race, deceased or living) and transplant characteristics (HLA mismatches, ischemic times, panel reactive antibody levels, time since transplant) will also be included. This will assist in making valid intervention effect estimates after accounting for baseline differences, as there may be patient-level differences between groups. The magnitude of between intervention differences on outcome variables (effect sizes) at each time point will be estimated using appropriate contrasts in the corresponding GLMM models.

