calibration (PSC).⁵⁷ We will assess the effect of the intervention on different sources of cost which include inpatient, outpatient and pharmacy in addition to the total aggregated cost. The cost models will be estimated using log-normal or gamma models (special cases of GLMM) to examine the association of the intervention with cost, adjusting for the aforementioned patient sociodemographics, donor information and transplant characteristics. Cost will be obtained from VINCI CDW and HERC as inpatient, outpatient, pharmacy and total aggregate for two years prior to the study period and for the two years of the intervention. We will also account for non-VA costs through linkage with CMS claims data. We will estimate different models adjusting for the clinical outcomes in order to examine the robustness of the results. GLMM allows for correlation between cost categories as well as for the likely skewed distribution of cost data. The Park test will be performed to check for the appropriate distribution of the cost data and AIC and BIC statistics for goodness of fit. Since, inpatient cost could exhibit a point mass of zero, we will use marginalized two-part models that are appropriate for semi-continuous data to model the relationship between the intervention and inpatient cost.^{58, 59} In general, statistical analyses will use two-sided tests with alpha set at 0.05.

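### The primary endpoint has no pre-study measurement, although cost does, so chance differences in site encounter rates go unadjusted with only five sites per arm

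*Combined protocol and SAP*

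**What the plan says.** **Cost.** Section 9.3.2 states that costs during the study "as well as those accrued in the 24-months prior to study initiation will be analyzed and compared between the control and intervention groups". Section 9.4 repeats that cost is obtained "for two years prior to the study period and for the two years of the intervention". The window is fixed by the calendar. Section 9.4 does not say what role pre-study cost plays: the adjusters named for the cost models are sociodemographics, donor information and transplant characteristics.

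**Primary endpoint.** Section 9.3.1 says of ER visits and hospitalizations: "These encounters will be captured electronically throughout the 24-month study through the use of the CDW". CMS claims are linked for non-VA encounters. No pre-study window is given. The primary model in Section 9.4 is a GLMM "with counts of these events as the outcome variable and intervention group (yes/no) as the primary independent variable". A second set of analyses adds age, sex, race, comorbidities, marital status, education, donor data and transplant characteristics including time since transplant. Prior utilization appears in neither.

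**Entry.** Section 4.2 says "There are no exclusion criteria for patients in this study as recruitment is at the level of the VA site" and "Patients may enter or exit the study in a rolling manner, which will be accounted for during analyses". There is thus no minimum time since transplant.

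**Randomization.** Ten sites, five per arm, are stratified by estimated size only, below 125 versus 125 or more (Section 9.2.1).

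**The concern.** With five clusters per arm, the two sets of sites can easily differ in their usual rate of ER visits and admissions, and size strata do little to prevent it. Prior utilization on the same scale would show such a difference and let the model allow for it. The plan pulls two years of earlier data for a secondary outcome but not for the primary one. At stake are precision and the credibility of the result: readers could not tell whether a modest difference in rates was already there before go-live.

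The cost baseline has a related weakness. A fixed calendar window combined with rolling entry means that the window contains the transplant operation for some patients and ends well before entry for others. Section 2.1 itself describes the break-even time as variable "due to high and varied peri-operative costs associated with this surgery". A raw comparison of pre-period cost between arms would partly reflect how many recent transplants each set of sites has.

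**Working it through.** **Inputs.** From Section 9.2: 1.269 ED visits per person-year, 25% relative reduction, ICC 0.05, N = 1,350 (675 per arm), 5 sites per arm, two-sided alpha 0.05, 80% power, Poisson test. From Section 3: 24 months of follow-up, taken as t = 2 years for every patient. Cluster size is 1,350/10 = 135.

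**1. The plan's own sample size.**
- Rates: 1.269 and 0.75 × 1.269 = 0.95175.
- Per arm before clustering: (1.960 + 0.842)² × (1/1.269 + 1/0.95175) / (ln 0.75)² / 2 = 87.2.
- Design effect: 1 + (135 − 1) × 0.05 = 7.7.
- Total: 2 × 87.2 × 7.7 = 1,343, against 1,350 stated. A rate-difference form gives 1,334.
- With 15% loss: 1,350/0.85 = 1,589, against 1,600 stated.

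The stated figures reproduce.

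**2. Chance difference between arms implied by the same inputs.**
- The design effect splits into a within-site part, 1 − 0.05 = 0.95, and a between-site part, 135 × 0.05 = 6.75.
- Expected events per arm at the control rate: 675 × 2 × 1.269 = 1,713.
- Between-site variance of the log rate ratio with no treatment effect: 6.75 × 2/1,713 = 0.0079; SD = 0.089; exp(0.089) = 1.09.
- So about one allocation in three would leave the arms' underlying rates more than about 9% apart. The target effect is ln 0.75 = −0.288, so one SD is 0.089/0.288 = 31% of it on the log scale.
- The between-site part is 6.75/7.7 = 88% of the variance, so what matters most is how well the prior rate predicts differences between sites.

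This takes no credit for the size strata or for covariates in the second set of analyses.

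**3. What a prior-rate covariate could gain.** The documents give no baseline-to-follow-up correlation r, so it is assumed over a range. The total variance is multiplied by (1 − r²), with N = 1,350.

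| r | Variance factor | Power, normal | Detectable reduction, normal | Power, t with 7 df |
|---|---|---|---|---|
| 0 | 1.00 | 80.2% | 24.9% | 67.5% |
| 0.3 | 0.91 | 83.8% | 23.9% | 71.5% |
| 0.5 | 0.75 | 90.0% | 21.8% | 79.4% |
| 0.7 | 0.51 | 97.6% | 18.1% | 91.9% |

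The last column uses a small-sample critical value for 10 sites with one site-level covariate. Without the covariate, t with 8 df gives 69.3%. On that basis the covariate costs about 2 points of power if r = 0, gains about 2 points at r = 0.3 and about 10 at r = 0.5.

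**4. What the fixed window covers.**
- A patient entering g months after initiation has (24 − g)/24 of their own prior 24 months inside it: 75% at month 6, 50% at month 12, 25% at month 18.
- A patient transplanted k months before initiation (k < 24) has the operation inside it, and (24 − k)/24 of it is pre-transplant: 75% at k = 6, 50% at k = 12.
- A patient transplanted during the study has a wholly pre-transplant window.

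The documents do not give the share of patients in each group.

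**The case against.** The plan does not ignore baseline. Elixhauser comorbidities and time since transplant are in the adjusted models, SRTR supplies donor, recipient and transplant characteristics (Section 10.1), and the Design and Outcomes summary promises adjustment for patient, provider and facility characteristics. It would be wrong to infer that cost is the only thing measured before the study; it is the only outcome measured then. The general promise does not fill the gap, because Section 9.4 lists no facility term and no prior utilization.

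A reader might infer that the missing baseline biases the primary comparison or invalidates the sample size. Neither follows. Randomization protects the comparison in expectation, the site random effect charges the test for between-site variation, and 1,350 reproduces without a baseline term. Nor is imbalance wholly invisible: pre-study inpatient cost by arm is an indirect signal of earlier hospitalization.

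A reader might also infer that the cost analysis will mistake the transplant leaving the window for savings. The documents state no before-after or difference-in-differences contrast, such a fall would occur in both arms, and the cost models adjust for time since transplant. Nor can a dollar size be attached, since neither the cost of a transplant episode nor the share of recent recipients is given.

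Finally, a window fixed before go-live has a real merit: it cannot contain intervention effects. Moving it to each late entrant's own start date would lose that. This stands, and the fix respects it.

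**Conclusion.** The point holds as a missed improvement to the primary analysis, not as an error in it. ER visits and hospitalizations have no pre-study measurement and no prior-utilization covariate, in a design where the plan's own inputs imply a chance difference between arms of about 9% (one SD) against a 25% target. That figure rests on the ICC of 0.05, the 1.269 rate, two full years per patient and equal site sizes. The power gain rests on an assumed correlation: useful from about 0.5 upward, small at 0.3, and slightly negative under a small-sample test if there is none. On cost, what is established is narrower: the role of pre-study cost is undefined, and the fixed window means different things for recent, late and long-standing recipients.

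**What to change.** **Sections 9.3.1 and 9.4, primary endpoint.**
- Pull ER visits and overnight hospitalizations from CDW and CMS for the same pre-go-live window as cost.
- Exclude the transplant admission and express the count per month observed.
- Prespecify this prior rate, with its functional form, as a covariate in the primary GLMM, not only in the second set of analyses.
- For patients with no usable pre-go-live history (recent recipients, late entrants), use the site's pre-go-live rate plus a missing-baseline indicator. No post-go-live data then enter the baseline, and every patient stays in the intent-to-treat analysis. The SAP must define usable history; the documents offer no basis for a particular minimum.

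**Sections 9.3.2 and 9.4, cost.** Keep the baseline before go-live, exclude the transplant admission, express it per month observed, and enter it as a covariate in the cost models instead of presenting a raw pre-period comparison.

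**Cost of the change.** Wording in three sections, one extra data pull from sources already being linked, and confirmation that the CMS request covers the pre-period. Recent recipients will have short or missing individual baselines, and a site-level term uses one of the few degrees of freedom that 10 sites provide.

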3 STUDY DESIGN

[figure not shown]
This is a 24-month prospective, parallel arm, cluster-randomized, controlled multicenter study in veteran organ transplant recipients receiving immunosuppressant medications through the VA system. The trial will randomize 10 VA sites, 5 to standard of care and 5 to standard of care plus the intervention. The intervention consists of a pharmacist-led health services endeavor utilizing a transplant medication dashboard system that monitors and reports on potential immunosuppression-related safety issues. The study will use prospective methodology to monitor patients for 24-months following site-randomization, comparing outcomes between the intervention and control sites. Clinical outcomes that will be assessed include health care encounters (hospitalizations and ER visits), estimated health care costs, and graft and patient survival. The functionality of the dashboard system will also be assessed by analyzing the proportion of actionable alerts created by the system as well as the proportion of missing labs, proportion of alarming lab values without follow up scheduled, estimated immunosuppression adherence (using the proportion of days covered [PDC]), proportion of significant drug interactions without an immunosuppressant level and the proportion of hospital and ER visits without follow up.

The study population will consist of veteran organ transplant recipients that receive immunosuppressant medications through the VA system. Organ transplant recipients will be identified using ICD-9/10 codes from the VA electronic health record. Once identified, active medications will be queried and those receiving immunosuppressant medications to prevent rejection (tacrolimus, cyclosporine, azathioprine, mycophenolate, sirolimus, everolimus, or belatacept) will be included in the study.

The study will take place at 10 VA sites, with 5 being randomized 5 to standard of care and 5 to standard of care plus the intervention. The 10 site locations are listed in the participating sites section of this protocol. After randomization and site initiation, all intervention sites will go live on the dashboard and pharmacist-led intervention simultaneously. Following this, patients at both the intervention and standard of care sites will be prospectively monitored for 24 months, in a parallel fashion.

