Another secondary outcome is to assess the success of the dashboard systems expansions and utilization. To do so, we will evaluate the dashboard's functionality by measuring and reporting descriptive statistics for the alert numbers, alert relevance, time and the actions taken with regards to the alert and the intervention magnitude. We will measure and report the time effort needed to conduct the interventions by study site pharmacists. Using REDCap, we will build an electronic data capture system, which allows the intervention pharmacists to efficiently enter alert and intervention information through a web-based portal, which will be housed within the VINCI environment. This information will be captured during the first 12 months of the intervention period, which will provide ample data without overwhelming the clinical pharmacists throughout the 24-month study. These measures will allow us to ascertain if the expanded dashboard is meeting expectations, with regards to functionality and efficiency. These measures will be assessed by investigators at quarterly intervals. If there is strong evidence to suggest particular components of the dashboard are not providing clinically relevant alerts or if the ratio of alerts to actionable alerts is exceedingly high, then the investigational team may decide to modify this component of the system. Thus, these

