process measures will serve to both assess the dashboard functionality and allow for modification to improve the efficiency of the intervention. The time assessment data will allow us to determine the amount of time and effort implementing this system requires, as it relates to embedding it into normal workflow processes. This information will be important if the dashboard is deemed effective and is disseminated for use to across the VA, as it will allow administrators to accurately assess the required pharmacist time needed for implementation. Finally, we will assess the type and magnitude of the interventions made using this dashboard to ensure study fidelity. The categorization and magnitude of these interventions will be assessed using the Overhage criteria, which is a well-established and validated method used in numerous studies, included several published by the investigators proposing this study.⁵² We will also assess the number of potential immunosuppression safety issues that occur and compare these between the two study arms. To do so, we will use the dashboard to provide monthly measurements of the following: percent of patients with missing laboratory assessments, percent of patients with alarming laboratory values without follow up scheduled, mean adherence to immunosuppression, based on refill timeliness and estimated using the PDC, percent of patients with a significant drug interaction without a immunosuppressant level and percent of patients with hospital discharge or ED visit without follow up scheduled. These will be measured in all patients and compared between the intervention and control groups at monthly intervals.

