For the assessment of the functionality of the dashboard and the time required to complete the intervention, there will be no comparisons or modeling within this analysis; we will utilize standard descriptive statistics for these measurements, including mean (SD), median (IQR), proportion (%) and 95% confidence interval. Variables assessed for this outcome will be captured through input into the REDCap database by intervention pharmacists during the first year of the intervention. We will compile the total number of alerts the dashboard system generates at each site and assess the proportion of these that were deemed clinical relevant and actionable by the pharmacists. We will also determine the mean/median time required to complete the intervention on a daily basis and estimate the time per 100 patient days. We will conduct these assessments concurrently on a bimonthly basis for the first year of the intervention, which will allow us to modify the dashboard system's reporting thresholds and improve functionality if deemed necessary by the investigational team. We will also assess the overall functionality of the dashboard at the end of the first year to determine composite metrics. Based on our experience with the current system, after an initial bolus effect, we expect the dashboard will produce two to three new alerts per 100 patient days with one to two of these being relevant and actionable. We will utilize 95% confidence intervals actual versus expected rates.

We will handle missing data using several techniques including multiple imputation and maximum likelihood.⁶⁰ Missing data mechanisms will be examined using both univariate and multivariate methods. We will check for missing at random (MAR) by creating a missing indicator for each missing variable and study the predictors of missingness using logistic regression. If any of the fully observed covariates or outcomes becomes significant in the missing data model then we will use methods for MAR if we do not have any reason to believe that the missing data mechanism is not at random. The proposed GLMM models, which are mixed effects models for the longitudinal data analyses, can handle data that are missing at random (MAR) and provide robust estimates. For the cross-sectional data analysis plan, we will use

multiple imputation approaches and for categorical missing data we will use latent class based multiple imputation.^{57,60}

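### The five medication-safety metrics are to be compared between arms month by month, up to 120 comparisons at 0.05, with no overall contrast, no multiplicity rule and no clearly assigned site-clustered model

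*Combined protocol and SAP*

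**What the plan says.** Section 9.3.2 has the dashboard give monthly values of five metrics. It begins with "percent of patients with missing laboratory assessments, percent of patients with alarming laboratory values without follow up scheduled". The other three are mean adherence by proportion of days covered, significant drug interactions without an immunosuppressant level, and discharges or ED visits without follow-up scheduled. The comparison rule is: "These will be measured in all patients and compared between the intervention and control groups at monthly intervals". No last month is named. Section 3 says that patients at both groups of sites "will be prospectively monitored for 24 months, in a parallel fashion".

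Section 9.4 assigns methods by type of outcome:

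- **Utilization:** "For comparative statistical assessments within the utilization outcomes, the two groups will be compared using a generalized linear mixed models (GLMM) approach". This model is described as handling clustering by site.
- **Cost:** log-normal, gamma or two-part models.
- **Dashboard functionality and pharmacist time:** description only, since "there will be no comparisons or modeling within this analysis".

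The five metrics are not named under any of these. One further sentence says that between-arm effect sizes "at each time point will be estimated using appropriate contrasts in the corresponding GLMM models". The significance level is general: "In general, statistical analyses will use two-sided tests with alpha set at 0.05".

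**The concern.** A monthly comparison of five metrics gives many arm differences and no single answer to whether the intervention improved medication safety. Nothing says in advance which month counts or how the months are to be combined, so the conclusion can be chosen after the data are seen. The same sites, and largely the same patients, are measured every month. A chance difference therefore tends to persist, and a run of significant months can look like a sustained effect.

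The metrics are a listed secondary objective (section 1.2). They are the plan's direct between-arm measure of immunosuppressant safety, which the general hypothesis in section 9.1 says will improve. They also feed the sixth planned manuscript in section 14. With only ten sites, it also matters that the model be stated.

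**Working it through.** The plan states no number of tests and no familywise error rate for these metrics, so there is no figure of its own to reproduce.

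**Inputs from the documents**
- 5 metrics, compared monthly (9.3.2).
- 24 months of follow-up (section 3). Using all 24 is an inference. The limit in "This information will be captured during the first 12 months of the intervention period" applies to the alert and intervention data that pharmacists enter in REDCap, not to these metrics.
- Two-sided alpha 0.05 (9.4).
- 10 sites, 5 per arm, averaging 169 patients.
- ICC 0.05, given in section 9.2 for the primary outcome only.

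**Assumptions:** the month-to-month correlation of site values, independence of the five metrics, and any ICC for these metrics.

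**1. Count and expected false positives.** 5 x 24 = 120 comparisons. If each test is valid at 0.05 and there is no effect, 120 x 0.05 = 6.0 are expected to be significant, whatever the correlation. If only 12 months were compared, 5 x 12 = 60 and 60 x 0.05 = 3.0.

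**2. Chance of at least one.** Null trials were simulated with 10 sites, 24 months, five independent metrics, equal correlation between any two months within a metric, and a two-sample t test on site values each month (8 df).

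| Month-to-month correlation | At least one of 120 significant |
|---|---|
| 0.5 | about 0.97 |
| 0.7 | about 0.89 |
| 0.9 | about 0.63 |
| 0.95 | about 0.51 |

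The mean stays at 6 throughout because false positives arrive in runs. At 0.9 the median is 2 and the chance of three or more is 0.46. At 0.95 the median is 1 and that chance is about 0.38. If the metrics are also correlated with each other at 0.5, the chance of any at month correlation 0.9 falls to about 0.55.

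**3. Worst case, if site were ignored.** The plan does not say this will be done. The design effect is DE = 1 + (m - 1) x ICC, and the true error of a nominal 0.05 test is 2 x (1 - Phi(1.96/sqrt(DE))).

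| m | ICC | DE | Error per test |
|---|---|---|---|
| 169 | 0.01 | 1 + 168 x 0.01 = 2.68 | 0.23 |
| 169 | 0.05 | 1 + 168 x 0.05 = 9.40 | 0.52 |
| 18 | 0.01 | 1 + 17 x 0.01 = 1.17 | 0.07 |
| 18 | 0.05 | 1 + 17 x 0.05 = 1.85 | 0.15 |

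The rows with m = 18 illustrate a metric whose denominator is patients with an encounter: 169 x 1.269/12 is about 18 ED visits per site-month. The rate is the one cited in section 9.2 from another cohort, so this too is an assumption.

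**4. One contrast per metric.** Five valid tests give 5 x 0.05 = 0.25 expected false positives. If independent, the chance of any is 1 - 0.95^5 = 0.226. Bonferroni would use 0.05/5 = 0.01 per metric. Across 120 monthly tests it would need 0.05/120 = 0.00042 each.

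**The case against.** The strongest reply is that section 9.4 already supplies the method. It presents the mixed model as handling site clustering, repeated measurements and binomial or Gaussian outcomes, which are the types these metrics need, and it takes effects at each time point from contrasts in the corresponding models. A clustered longitudinal model with monthly contrasts is a reasonable reading. This stands as far as clustering goes: the gap there is unclear scope, not a plan to ignore site. It does not settle the rest, because that reading still yields one contrast per month and no overall answer.

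Three other points hold in part:

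- Section 9.3.2 says that the arms are compared; it does not say that each month is tested at 0.05. The count of 120 is therefore an upper figure.
- These are secondary process measures. None is named among the three main hypotheses in section 9.1, and section 14 calls the relevant paper descriptive.
- Formal multiplicity control across secondary process measures is partly a matter of preference.

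A reader might infer two stronger claims. One is that chance will certainly produce several significant months. Six is only an average: with valid tests, about 37% of null trials show no significant month at correlation 0.9, and about half show none at 0.95. The other is that some 28 to 63 of the 120 comparisons will be falsely significant (120 x 0.23 and 120 x 0.52). That describes an analysis ignoring site, which no section plans. It also applies the full 169 patients per site to every metric, although some may have smaller denominators.

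**Conclusion.** The concern holds in limited form. The stated monthly comparison gives up to 120 between-arm comparisons with no pre-specified summary and no multiplicity rule, and the model for them has to be guessed. Under valid site-level tests and no effect, 6 are expected to be significant on average, and the chance of at least one runs from about half to 97% over month-to-month correlations of 0.95 down to 0.5. Those chances rest on assumed correlations and on independent metrics; correlated metrics lower them. The per-test errors of 23% to 52% are a worst case that would arise only if site were ignored at ICC 0.01 to 0.05 with 169 patients per site.

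This should be changed, because a better analysis is available within the methods the plan already uses. It does not touch the primary or cost analyses.

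**What to change.** In sections 9.3.2 and 9.4, replace the monthly comparison with one longitudinal GLMM per metric. Include a site random effect, a patient random effect where the data are at patient level, month, arm and the randomisation stratum, with small-sample degrees of freedom suited to ten sites. Pre-specify one contrast per metric: the average arm difference over the 24 months. Name the five metrics in 9.4 so that the scope of the model is not in doubt, and state the last month and each metric's denominator. Show monthly values by arm as a plot or table without tests. Holm or false-discovery control across the five contrasts is optional; say either way.

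The cost is SAP wording and five models, with no new data. The small downside is that no single month can be claimed as significant.
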